Calcium Electroporation for Treatment of Cutaneous Metastases; randomized double blind phase II study

NCT03628417

Primary Completion Date: 04/06/2019

Last update: 03/10/2019

Last release: 09/24/2019

Introduction

Background

Electroporation is a method that can facilitate transport of molecules across the cell membrane and into the cell by means of electrical pulses. The method can be used with molecules that normally have difficulty passing the cell membrane such as chemotherapy (electrochemotherapy). Electrochemotherapy (ECT) is used in cancer therapy, where chemotherapy is administered intratumoral or intravenous, then followed by electrical pulses applied directly on the tumor. The chemotherapy accumulates in the cancer cells which results in an increased cytotoxic effect. The most used chemotherapeutic drug used in electrochemotherapy is bleomycin. Electrochemotherapy is a well-documented local treatment form for especially cutaneous tumors. Today, the treatment is used mostly in palliative care in more than 140 centres around Europe.

In vitro and *in vivo* studies have shown that the combination of calcium and electroporation is an effective method in killing cancer cells without serious side effects. This new combination opens the possibility of replacing bleomycin with calcium in treatments with electroporation.

Calcium electroporation is a local treatment where calcium is administered intratumoral and followed by electrical pulses applied on the tumor.

Calcium electroporation would be possible to use on patients for whom chemotherapy is contradicted e.g. severe lung functions impairment, pregnant woman etc. Calcium electroporation is a simple and inexpensive cancer treatment that does not involve any administration of cytotoxic chemotherapy, and can be performed by surgeons, radiologists as well as oncologists. Both electroporation equipment and calcium are already being used in the clinic, so the treatment can easily be implemented.

Method

We wish to examine calcium electroporation on patients with cutaneous metastases from any histology and compare the effect with electrochemotherapy. On evaluations on tumor response we want to investigate if calcium can replace bleomycin in the treatment of cutaneous metastases.

To investigate that we use a randomized double blinded phase II study on patients with small cutaneous metastases. The metastases will be randomized into two treatment arms:

1. Intratumoral injection with calcium, followed by electrical pulses.
2. Intratumoral injection with bleomycin, followed by electrical pulses.

Randomization will be done separately on each metastasis

Objectives

Primary Objective

The primary objective is to evaluate and compare response rate of calcium electroporation and electrochemotherapy on cutaneous metastases. Response will be evaluated individual on each treated metastasis by clinical examination and documented by clinical photo before and after treatment. Evaluation is performed according to RECIST-like guidelines.

Secondary Objective

The secondary objective is to register adverse events for calcium electroporation and electrochemotherapy respectively. Adverse Events (AE) and Serious Adverse Events (SAE) will be evaluated and graded according to Common Terminology Criteria for Adverse Events (CTCAE) version 4.0.

Tertiary Objective

The tertiary objective is to register if calcium affects the current strength in electroporation treatments. Maximum given current in metastases treated with calcium will be compared to maximum given current in metastases treated with bleomycin.

Trial Design

Trial Design for Treatment of Cutaneous Metastases

It is a randomized double blinded phase II study (adapted from Denmark) comparing the effect of calcium electroporation with ECT with bleomycin on patients with cutaneous metastases of any histology. As calcium and bleomycin are administered intratumoral, only small metastases from 0.5-3cm will be treated. The treatments will be compared in tumor response and adverse events. Treatment will be done in a palliative purpose.

Cancer patients with cutaneous involvement have often several metastases. A maximum of ten metastases will be included per patient. One to six metastases (depending on the patient's number of metastases) will be numbered 1-6 and randomized into one of two treatment arms:

1. Intratumoral calcium followed by electroporation
2. Intratumoral bleomycin followed by electroporation

Randomization will be performed separately on each metastasis, so the patient may receive both treatments. Calcium and bleomycin will be mixed into syringes labeled with numbers according to the metastases and both treating doctor and patient will be blinded to the content of the syringes.

If the patient has more than six metastases, then one to four metastases will be used for biopsy. The treatment of these metastases will be known, and biopsies will be performed before and after treatment. The metastases used for biopsy will not be evaluated on response.

- One to six metastases: All metastases will be evaluated on response, no biopsies.
- Seven metastases: six metastases will be evaluated on response and one metastasis will be used for biopsy before and/or after treatment with calcium.
- Eight Metastases: six metastases will be evaluated on response and two metastases will be used for biopsy before and/or after treatment with calcium and bleomycin respectively.
- Nine Metastases: six metastases will be evaluated on response and three metastases will be used for biopsy before and/or after treatment with calcium and bleomycin respectively.
- Ten Metastases: six metastases will be evaluated on response and four metastases will be used for biopsy before and/or after treatment with calcium and bleomycin respectively.

The treatment will be performed in local or general anesthesia depending on location and number of metastases. Bleomycin/calcium will be administered intratumorally and immediately after the electrode will be placed on the metastasis. The electric pulses are generated using a cliniporator according to ESOPE (European Standard Operating Procedure of Electrochemotherapy). It is a once only treatment and the patients will be followed up with regular clinical controls for six months. At follow up six months after treatment, the randomization code for the one patient will be revealed. If the patient agrees, biopsies will then be taken from an area treated with calcium and an area treated with bleomycin. Last visit will be one year after treatment.

To identify the metastases at follow up visits, the metastases will be marked with a pen, numbered and documented with clinical photos at baseline.

Randomization

The metastases are randomized by block randomization and are done separately in each patient. The randomization is performed by an extern unit, using the computer program nQuery Adviser 7.0. The bleomycin and calcium are mixed and labeled by an extern unit, and since both calcium and bleomycin are transparent and identical in volume, it is possible to label the syringes in a manner to blind the treating doctor. The syringes are labeled with numbers according to the metastases so syringe number '1' goes to metastasis number '1' and so on. The randomization code is kept behind locked doors, and is not accessible to the treating doctor. The randomization code is revealed for each patient after follow up, 6 months after treatment.

The randomization code can be revealed before completion of the investigation, if the investigator believes that the treatment causes so serious unexpected events or reactions, that a continuation of treatment is unacceptable.

As the randomization is done separately in each patient, it is possible to break the code for the individual patient, without breaking the code of the other participants.

Dose

The dose of calcium chloride was amended to 220 mmol/L from 168 mmol/L in this trial.

Volume of calcium chloride is dependent on tumor volume. Smaller tumors should have bigger volume per cm^3 , as smaller tumors are expected to have a bigger loss of injected medicine into the surrounding tissue. The dose volume is calculated according to the 'European Standard Operating Procedure of the Electrochemotherapi (ESOPE)':

Calcium

Calcium chloride 220 mmol/L (9 mg/ml):

- Tumor $< 0,5 \text{ cm}^3$ – 1 ml / cm^3 tumor volume
- Tumor $> 0,5 \text{ cm}^3$ – 0,5 ml/ cm^3 tumor volume

Tumor volume = $ab^2\pi/6$ (a=longest diameter, b= longest diameter perpendicular to a)

Bleomycin

Both dose and volume of bleomycin is standard according to ESOPE

Bleomycin 1000 IU/ml:

- Tumor $< 0,5 \text{ cm}^3$ – 1 ml / cm^3 tumor volume
- Tumor $> 0,5 \text{ cm}^3$ – 0,5 ml/ cm^3 tumor volume

Tumor volume = $ab^2\pi/6$ (a=longest diameter, b= longest diameter perpendicular to a)

Maximum of injected bleomycin per tumor will be 1500 IU and total dose per treatment 7500 IU. Normal maximum limit for bleomycin is 15.000 IU/ m^2 body surface area.

Bleomycin and calcium chloride are mixed and labeled according to current guidelines. The mixtures will be used in a maximum of 6 hours after mixing.

The Electrical Pulses

The generation of electrical pulses is performed using a Cliniporator (IGEA, Italy). It is possible to use a plate or needle electrode. Needle electrodes are of different shapes e.g. linear or hexagonal, with different lengths and spacing between pins. The Cliniporator generates 8 pulses with duration of 0,1 ms and 400 V at a frequency of 5 kHz with linear electrodes, and 4 pulses with duration of 0,1 ms and 730 V at a frequency of 5 kHz with hexagonal electrodes. The individual electrode is selected according to tumor size and localization. Cliniporator and electrodes are CE marked.

Anesthesia

The patients are anesthetized during treatment with local or general anesthesia. The anesthesia is planned in consultation between doctor and patient.

Biopsy

If the patient agrees biopsies will be performed from the tumor area before and after electroporation during local anaesthesia.

Patients with more than 6 metastases:

- One to two biopsies before treatment
- One to two biopsies one week after treatment from metastases treated with calcium and bleomycin respectively.

All patient's regardless number of metastases will have done one biopsy from area treated with calcium and one from area treated with bleomycin, after the randomization code is revealed.

All biopsies will be handled according to current guidelines and analyzed by a pathologist for amount of tumor tissue, inflammation, fibrosis and necrosis.

Duration

The treatment itself lasts a total of 30 to 60 minutes, depending if the patient receives local or general anesthesia. The patient will then be followed for up to 12 months with regular visits.

Stop Rules

The trial may be interrupted prematurely if:

- Treatment causes such severe side effects that a continuation of treatment is unacceptable
- Enrollment is too low to expect completion of the trial in its current form.

The Research Ethics Committee and the Medicines Agency will be informed about the end of the trial.

Statistical analysis

This is a randomized non-inferiority study comparing calcium electroporation with electrochemotherapy with intratumoral injection of bleomycin. For dimensioning tumor number, analysis of non-inferiority study is used. Tumor response is evaluated at each follow up with surveying. Documentation is done with digital color photography, including a ruler to estimate tumor size. Primary evaluation of the response will be based on criteria similar RECIST guidelines 1.1. Tumor response was analyzed using Fisher's exact test on objective response 6 months after treatment.

Response rate of tumors ≤ 3 cm treated with ECT with bleomycin is 85-100% (existing data). In this study, we have chosen not to put the expected response rate for ECT too high, but estimate it to 85%. We have no clinical results for the treatment of calcium electroporation, but on the basis of preclinical studies, the response rate for calcium electroporation is estimated to 70%. In order to detect a clinical difference in the two treatments of 15%, with a significant level of 0.1, and a power

of 80%, a minimum of 34 evaluable tumors need to be included. (Sample Size Calculator: https://www2.ccrb.cuhk.edu.hk/stat/proportion/tspp_sup.htm)

The metastases are evaluable 4 weeks after treatment. If a patient is excluded from the protocol before 4 weeks follow up, the patient will be replaced.

The number of patients that are being pulled out of the trial will be listed and primary reason for the exclusion will be described.

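### Openly treated biopsy lesions in patients with more than six metastases could help the treating doctor guess the drug in the six blinded lesions

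*Combined protocol and SAP*

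**What the plan says.** The section on trial design for cutaneous metastases randomizes up to six lesions per patient, each treated from a numbered syringe, and states that "both treating doctor and patient will be blinded to the content of the syringes". The Randomization section describes the masking: an external unit prepares the syringes, the two liquids match in appearance and volume, and the code is locked away and opened per patient at 6 months.

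The design section then adds a second group of lesions: "If the patient has more than six metastases, then one to four metastases will be used for biopsy". For these, "The treatment of these metastases will be known, and biopsies will be performed before and after treatment", and "The metastases used for biopsy will not be evaluated on response". With seven metastases, "one metastasis will be used for biopsy before and/or after treatment with calcium". With eight, "two metastases will be used for biopsy before and/or after treatment with calcium and bleomycin respectively"; the entries for nine and ten name both drugs in the same way. The section also says "It is a once only treatment and the patients will be followed up with regular clinical controls for six months". The Biopsy section adds "One to two biopsies one week after treatment from metastases treated with calcium and bleomycin respectively".

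Under the primary objective, response is judged lesion by lesion on clinical examination and documented by photograph. No separate or blinded assessor is named. The Statistical analysis section compares objective response at 6 months with Fisher's exact test and asks for at least 34 evaluable tumours.

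**The concern.** Masking the syringes protects the blind only until injection. After that, anything that can be observed on a lesion and that depends on the drug is a potential cue. In a patient whose lesions are all coded, a doctor may notice that some behave differently but has no labelled lesion to show which drug is which. A labelled lesion in the same patient can supply that.

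The person most exposed is the treating doctor, who on this text may also judge response. Because the endpoint is a clinical judgement, a guess about the drug could influence the score. Adverse event grading, the secondary objective, is exposed in the same way. The labelled lesions are not scored for response, so any effect on the primary comparison is indirect, through lesions 1-6.

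**Working it through.** The plan states no figure on this point, so most of the check sets its provisions side by side. The only arithmetic concerns scale.

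**1. Are open and blinded lesions together?** The design section places both in the same patient. Treatment is given once and no separate session is described, so the natural reading is one session and one follow-up period.

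**2. What does the open group reveal?**

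| Metastases | Blinded lesions | Open lesions | Known reference |
|---|---|---|---|
| 1-6 | 1-6 | 0 | none |
| 7 | 6 | 1 | calcium only |
| 8 | 6 | 2 | both drugs |
| 9 | 6 | 3 | both drugs |
| 10 | 6 | 4 | both drugs |

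**3. Is there a possible cue?** The tertiary objective compares the maximum current between calcium and bleomycin lesions, so the plan treats a drug difference in current as an open question. Masking by appearance and volume does not cover it. Local reaction is another conceivable cue, but no visible drug difference is predicted anywhere.

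**4. When is it available?** The current is available at treatment. The open lesions are seen again at the one-week biopsy. Both come before the 4-week point at which lesions become evaluable and before the 6-month analysis.

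**5. Could one guess inform others?** Allocation is blocked within each patient, and the block size is not stated. For six lesions, as assumed examples:
- one block of 6 (3:3) leaves C(6,3) = 20 sequences;
- three blocks of 2 leave 2^3 = 8;
- no restriction leaves 2^6 = 64.

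Under either blocked scheme, a correct guess on some lesions narrows the choice for the rest.

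**6. How much of the trial is exposed?** Reading 34 as the total, and taking six lesions per affected patient:
- one patient: 6/34 = 17.6%;
- two patients: 12/34 = 35.3%;
- three patients: 18/34 = 52.9%.

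The expected number of such patients is not given and could be zero. Assuming 1:1 allocation (17 per arm), one re-scored lesion moves that arm's response rate by 1/17 = 5.9 points. The planned 15-point difference equals 0.15 × 17 = 2.55 lesions. These figures show how sensitive the comparison is; they do not estimate a bias.

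**7. Does the plan need the open label?** The biopsy lesions do not enter the response endpoint, and histology can be matched to drug once the code is released. There is one practical need. With nine or ten metastases there are three or four biopsy lesions, but only one to two post-treatment biopsies at one week. Someone must therefore know the drugs to choose a lesion of each. The external unit can do this.

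**The case against.** The strongest reply is that the blind is not broken. The blinding statement concerns the numbered syringes for the randomized lesions, whose code stays locked, and the design section expressly treats the biopsy lesions as a separate group. That stands. A reader might infer that the two provisions contradict each other, or that the doctor is certainly told the drug. The text does not say to whom the treatment is known. That the doctor knows is the natural reading, because no exception is made, but it remains an inference.

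The cues are also uncertain. A reader might take the biopsy plan as evidence that tissue reaction differs by drug. It lists only what a pathologist examines in all biopsies and predicts no difference. Current may vary with electrode type and voltage, which depend on tumour size and site, so one or two reference lesions may not be comparable with lesions 1-6. Biopsy itself disturbs the local reaction. These points stand and rule out any claim that unmasking will occur.

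A reader might also try to size the bias, for instance by supposing that 1 in 10 exposed lesions in one arm is re-scored. With one to three affected patients that gives 0.176 × 10 = 1.8 to 0.529 × 10 = 5.3 points. The rate has no source, and with 3 to 9 exposed lesions in an arm (1:1) it amounts to only 0.3 to 0.9 of a lesion. The direction is unknown too, and in a non-inferiority comparison direction decides whether the claim is helped or harmed. The figure should not be used.

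Finally, if current or reaction does differ by drug, a doctor treating a mixed set of lesions 1-6 sees that contrast anyway. This is right, but without a labelled lesion the contrast is harder to attribute to a particular drug.

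**Conclusion.** The point holds as a possible, indirect weakness in the blinding that is cheap to remove. By a stated rule, the plan puts openly treated lesions beside six blinded ones in the same patient, and it names no separate blinded assessor for an endpoint judged by clinical examination. Both drugs are known references with eight to ten metastases, and calcium alone with seven.

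The conclusion assumes that the treating doctor learns the biopsy-lesion drug and also scores response; the documents neither confirm nor exclude either. No size of bias can be given. The exposure is up to 6 of 34 tumours (18%) per affected patient. A reader might infer that these patients weigh most in the primary comparison. They do not stand out: a patient with exactly six metastases also supplies six randomized lesions and has no open lesion.

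**What to change.** For patients with eight to ten metastases, replace the first clause of the sentence "The treatment of these metastases will be known, and biopsies will be performed before and after treatment" with wording to this effect:

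- The external unit assigns the biopsy lesions so that both drugs are represented, in random order, and supplies coded syringes for lesions 7-10.
- The external unit names, by lesion number, which lesions to biopsy at one week, so that both drugs are sampled.
- The treating doctor, the patient and the pathologist stay blinded to this code until the 6-month response is recorded. Biopsies are matched to drug at analysis.

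For patients with seven metastases, choose one of two options and state it. Either the external unit assigns the single biopsy lesion by chance under the same code, or the planned allocation stays and the protocol acknowledges that a single-drug reference remains.

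The cost is protocol wording, up to four more coded labels per patient, and a short list of lesion numbers from a unit already preparing numbered syringes. Assigning the seventh lesion by chance would yield fewer calcium biopsies.

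The change removes the labelled references. It does not remove any cue visible among lesions 1-6 themselves. To cover that as well, the ruler photographs already planned could be read by someone who was absent at treatment and has seen neither the current readings nor the biopsy-lesion drugs. That would need a reader's time.

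### Tumour size is measured on every metastasis to set the injected volume, but the plan states no use of it in allocation or in the response comparison: an avoidable chance imbalance and a modest loss of precision

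*Combined protocol and SAP*

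**What the plan says.** **Dose section.** "Volume of calcium chloride is dependent on tumor volume", and tumour volume is computed from two perpendicular diameters. Both agents follow the same rule: "1 ml / cm^3 tumor volume" below 0.5 cm3 and "0,5 ml/ cm^3 tumor volume" above it. The reason given is "Smaller tumors should have bigger volume per cm^3 , as smaller tumors are expected to have a bigger loss of injected medicine into the surrounding tissue". For bleomycin only, the section adds: "Maximum of injected bleomycin per tumor will be 1500 IU and total dose per treatment 7500 IU".

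**The Electrical Pulses.** The electrode is chosen by tumour size and location. Linear and hexagonal electrodes deliver different pulse numbers and voltages.

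**Trial Design.** Metastases of 0.5-3 cm are treated. "One to six metastases (depending on the patient's number of metastases) will be numbered 1-6 and randomized into one of two treatment arms". No order for the numbering is given.

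**Randomization.** "The metastases are randomized by block randomization and are done separately in each patient". Block length and any size stratum are not stated. An external unit prepares and labels the syringes, and the section describes the two agents as equal in volume.

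**Statistical analysis.** "Tumor response was analyzed using Fisher's exact test on objective response 6 months after treatment". No covariate, stratum, subgroup or sensitivity analysis by size is given.

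**The concern.** Size governs both halves of the treatment, the injected volume and the electrode, and the protocol itself expects it to affect how much drug stays in the tumour. It is therefore a plausible predictor of response, and it is known before the syringes are prepared. Blocks within patient balance the number of lesions per arm. They do not control which lesions go to which arm, so one patient's larger metastases can fall mostly on one side. With about 17 tumours per arm such imbalances are not rare, and the stated test cannot take account of them. What is at stake is some precision, and how easily a small trial's result can be read if the arms turn out visibly unlike in size.

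**Working it through.** **1. The plan's sample size.** The Statistical analysis section gives 34 evaluable tumours from response rates of 85% and 70%, a 15-point difference, significance level 0.1 and power 80%. One-sided, with unpooled variance and 1:1 allocation (sidedness and ratio are assumptions):

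n per arm = (1.2816 + 0.8416)² × (0.85×0.15 + 0.70×0.30) / 0.30² = 4.508 × 0.3375 / 0.09 = 16.9, so 17 per arm and 34 in total.

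This matches, but only if the expected difference is added to the margin (0.15 + 0.15). That is a separate question. Here 34 is used only as the trial's size.

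**2. Do both dosing bands occur?** For a sphere V = πd³/6. At d = 0.5 cm, V = 0.065 cm3; at d = 3 cm, V = 14.1 cm3. The 0.5 cm3 boundary lies at d = 0.98 cm, well inside the eligible range, so both bands can be expected.

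**3. How often are the arms unlike in size?** Assumptions: 8 patients with 4 tumours and 1 with 2, balanced within patient; 40% of tumours above 0.5 cm3; correlation of size within patient (on a latent normal scale) of 0, 0.3 or 0.6. Each arm has 17 tumours, so a difference of 15 points or more means at least 3 tumours (3/17 = 17.6 points).

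| Within-patient size correlation | Trials with imbalance of 15 points or more, blocks as planned | Same, consecutive size pairs |
|---|---|---|
| 0 | about 39% | about 24% |
| 0.3 | about 33% | about 20% |
| 0.6 | about 25% | about 15% |

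Other assumed patient mixes (7 or 12 patients, 30% or 50% large, correlation 0 or 0.3, correlation defined differently) give imbalances of 20 points or more in about 11-24% of trials as planned and about 3-15% with pairing. The gain is smaller when many patients have a single lesion.

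**4. What does an imbalance do to the result?** Shift in the arm difference = imbalance × gap in response between bands. The documents give no gap, so a range is shown.

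| Assumed gap | 15-point imbalance | 20-point imbalance |
|---|---|---|
| 10 points | 1.5 | 2 |
| 20 points | 3 | 4 |
| 30 points | 4.5 | 6 |

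**5. Compared with ordinary sampling error.** SE of the difference = √[(0.85×0.15 + 0.70×0.30)/17] = √(0.3375/17) = 0.141, or about 14 points. At an assumed 25-point gap, size pairing lowers the standard deviation of the arm difference from about 0.139 to at best 0.135.

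**The case against.** The case for leaving the plan alone is good, and most of it stands.

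- **No systematic bias.** Allocation is random, so chance imbalance in size is already within the test's error rate. The volume-per-cm3 rule is the same in both arms. A reader might infer that the halving at 0.5 cm3 itself favours one treatment; nothing in the rule does.
- **The effect is small.** A reader might infer that size imbalance could move the result by something like the 15 points the trial is planned around. The arithmetic does not support that: 3-6 points needs both a 15-20 point imbalance and an assumed 20-30 point response gap.
- **The gap is not documented.** The size-dependent dosing is meant to compensate for drug loss in small tumours, which does not show that response differs by size. The plan quotes a single bleomycin response range, 85-100%, for all tumours up to 3 cm.
- **Silence on numbering is not a rule.** The plan does not say that size is disregarded when lesions are numbered; it states no order.
- **Remedies have limits.** Pairing cannot help patients with one lesion, and within-band counts will be thin: about 7 larger tumours per arm (0.40 × 17) and about 8 non-responders overall (17×0.15 + 17×0.30 = 7.65).

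What remains is that a baseline value already collected, and treated by the protocol as relevant to drug retention, has no stated role in allocation or analysis when giving it one costs very little.

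The bleomycin maximum is a related loose end. At 1000 IU/ml, 1500 IU is 1.5 ml, reached at 3 cm3 (1.79 cm for a sphere). No maximum is stated for calcium, yet the agents are described as equal in volume. A reader might infer that the arms are dosed differently in large tumours, or that blinding fails there. The text settles neither.

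**Conclusion.** The point holds as an optional efficiency improvement. The plan measures size on every lesion, lets it determine injected volume and guide electrode choice, and states no use of it in allocation or in the response test. The consequence is an avoidable chance imbalance (15 points or more in about 25-39% of trials) and a modest loss of precision. The likely shift of about 3-6 points is well below the standard error of about 14. These figures rest on assumed patient mix, share of larger tumours, within-patient correlation and response gap; at a 10-point gap the shift is only 1.5-2 points. The documents do not support calling the comparison biased or the test invalid.

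**What to change.** **(a) Allocation.** Number each patient's metastases in order of measured volume, and have the external unit allocate one of each consecutive pair (1-2, 3-4, 5-6) to each arm; allocate an unpaired last lesion at random. Cost: a numbering instruction and a paired list. Smaller blocks are more predictable, which matters little while an external unit holds the list and labels the syringes.

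**(b) Analysis.** Prespecify a response comparison stratified by the baseline dosing band (below or above 0.5 cm3) that also accounts for patient, since the blocks are formed within patient. One option is a Mantel-Haenszel difference over the two bands, tested by repeating the within-patient allocation. Report response by arm within band descriptively only, because counts will be sparse. This also covers single-lesion patients, whom pairing cannot balance. Cost: a few sentences, no new data. If allocation is already complete, only (b) remains, labelled as supportive.

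**(c) Text.** Reconcile the per-tumour maximum stated only for bleomycin with the statement that the two agents are equal in volume.

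None of this changes a dose, a visit or the number of lesions.

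### The plan declares non-inferiority but names only Fisher's test of equal response rates, with no labelled margin, confidence bound or success rule

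*Combined protocol and SAP*

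**What the plan says.** All references are to the Combined protocol and SAP.

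- **Framework** (Statistical analysis): "This is a randomized non-inferiority study comparing calcium electroporation with electrochemotherapy". The tumour number is attributed to the same framework: "For dimensioning tumor number, analysis of non-inferiority study is used".
- **Analysis** (Statistical analysis): "Tumor response was analyzed using Fisher's exact test on objective response 6 months after treatment". No other analysis of tumour response is named.
- **Sizing** (Statistical analysis): bleomycin is put at 85% and calcium at 70%. The sizing sentence then opens "In order to detect a clinical difference in the two treatments of 15%, with a significant level of 0.1", with 80% power and at least 34 evaluable tumours. It does not say whether 0.1 is one- or two-sided, or whether 34 is a total or a number per arm.
- **Question** (Method): "we want to investigate if calcium can replace bleomycin in the treatment of cutaneous metastases".
- **Objective** (Primary Objective): "The primary objective is to evaluate and compare response rate of calcium electroporation and electrochemotherapy on cutaneous metastases".
- **Unit of randomisation** (Trial Design): "Randomization will be performed separately on each metastasis, so the patient may receive both treatments".

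No section labels a figure as a non-inferiority margin, states a non-inferiority hypothesis, asks for a confidence interval or bound, or says which result would support non-inferiority.

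**The concern.** Three parts of the plan should express one hypothesis, and they do not. The declared framework is non-inferiority, the sizing sentence speaks of detecting a difference, and the test addresses equality. A significant Fisher result shows only that the rates differ. A non-significant one says nothing about how much worse calcium might be.

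The clinical question is whether calcium can take bleomycin's place. A trial that is called non-inferiority but has only an equality test invites the reader to take a non-significant p-value as support for replacement. In a small trial that outcome is likely even when calcium is clearly worse, and the smaller the trial, the likelier it becomes.

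**Working it through.** **Inputs.** From Statistical analysis: bleomycin 85%, calcium 70%, difference 15 points, level 0.1, power 80%, 34 tumours. Assumed: 1:1 allocation and independent lesions. Because the plan leaves both points open, results are given for 17 and 34 per arm and for one- and two-sided 0.1.

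**1. The plan's own figure.** The normal-approximation non-inferiority formula per arm is

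n = (z₁₋α + z₀.₈)² × [p_B(1−p_B) + p_C(1−p_C)] / (p_C − p_B + margin)².

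With one-sided 0.1, (1.2816 + 0.8416)² = 4.508. The variance sum is 0.85×0.15 + 0.70×0.30 = 0.3375.

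- *Rates as documented, 15 points as margin:* the denominator is (−0.15 + 0.15)² = 0, so no finite n exists.
- *Rates reversed (calcium 85%, bleomycin 70%), same margin:* 4.508 × 0.3375 / 0.30² = 16.9, so 17 per arm and 34 in total. This matches the stated figure, but only with calcium assumed 15 points better, the opposite of the text.
- *Detecting a 15-point difference from equality:* 4.508 × 0.3375 / 0.15² = 67.6, so 68 per arm (136 in total). With a pooled variance it is 138 in total at one-sided 0.1 and 190 at two-sided 0.1.

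With the rates as documented, neither a non-inferiority test at 15 points nor an equality test gives 34.

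**2. What a non-significant Fisher result is worth.** By full enumeration,

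P(non-significant) = Σₓ Σᵧ Bin(x; n, 0.85) × Bin(y; n, p_C) × 1[Fisher p > 0.1].

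The comparator is a score test of the hypothesis that calcium is worse by 15 points or more (Farrington-Manning). Here Z = (observed calcium − observed bleomycin + 0.15) / SE, with SE from constrained maximum likelihood, and non-inferiority is declared if Z > 1.2816.

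| True calcium rate | n per arm | Fisher non-significant, one-sided 0.1 | Fisher non-significant, two-sided 0.1 | Score test declares non-inferiority |
|---|---|---|---|---|
| 70% | 17 | 74% | 84% | 10% |
| 70% | 34 | 53% | 67% | 10% |
| 55% | 17 | 38% | 53% | 1.3% |
| 55% | 34 | 10% | 20% | 0.4% |

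**3. One example.** Take 15/17 responses on bleomycin and 11/17 on calcium (88% against 65%). Fisher's p is 0.22 two-sided and 0.11 one-sided, so the result is non-significant on both readings. The difference is 11/17 − 15/17 = −0.235. A simple Wald standard error is √(0.882×0.118/17 + 0.647×0.353/17) = 0.140. The one-sided 90% lower bound is therefore −0.235 − 1.2816×0.140 = −0.41. These data are compatible with calcium being about 41 points worse.

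**4. What a proper non-inferiority test would deliver (assumed 15-point margin).**

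- Both true rates 85%, one-sided 0.1: declared in 44% of trials at 17 per arm and 67% at 34 per arm. For 80% power, n = 4.508 × 2×0.85×0.15 / 0.15² = 51.1, so 52 per arm.
- If 0.1 is two-sided, the bound is one-sided 0.05: about 30% at 17 per arm and 52% to 53% at 34 per arm, depending on the interval method. For 80% power, (1.6449 + 0.8416)² × 0.255 / 0.0225 = 70.1, so 71 per arm.
- The plan's 85% against 70%, one-sided 0.1: about 10% at any size, because the true deficit sits on the margin.

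**The case against.** The strongest reply is that a margin exists but is not labelled. The section says non-inferiority analysis set the tumour number, and 15% is the only clinical difference it gives. Using 15 points as a margin at one-sided 0.1 returns exactly 34 in total. That is a fair reading of where the number came from, and it makes 17 per arm with one-sided 0.1 the likelier of the readings above. It does not rescue the plan. The match needs the arm rates reversed, the text calls 15% a difference to detect, and Fisher's test would not use the margin even if it were granted.

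Second, the pass rates in the table measure a rule the plan never states. This stands: they show the size of a possible misreading and are not the plan's error rate. The objective of evaluating and comparing could be met by reporting both rates. But the plan also declares non-inferiority and gives no other basis for concluding it.

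Third, every figure here treats lesions as independent, although up to six per patient are randomised. This also stands. Clustering and the 80% power claim are separate weaknesses, and the mismatch between hypothesis and test does not depend on either.

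Fourth, the document shows a primary completion date in 2019 and describes the analysis in the past tense, so a margin may no longer be one that can be fixed in advance. That affects which remedy is usable, not whether the defect is there.

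**Conclusion.** The concern holds, and it must be fixed because it lies in the primary analysis. The declared hypothesis is non-inferiority, the only test is of equality, and nothing links the two. If followed exactly, the plan cannot establish non-inferiority whatever the data show.

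On every reading of the two unstated items, a true 15-point deficit is more likely than not to give a non-significant Fisher result: from 53% (34 per arm, one-sided) to 84% (17 per arm, two-sided). That rests on bleomycin at 85%, 1:1 allocation and independent lesions. The lower end is only just above one half and should not be pressed harder than that. The mismatch itself needs no numerical assumption.

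**What to change.** **If a margin can be justified and fixed before unblinding.** Make the primary analysis the calcium-minus-bleomycin difference in objective response at 6 months, with a one-sided lower confidence bound at the 0.1 level (a 90% bound), and state the sidedness explicitly. Use a small-sample score-type method whose variance allows for several lesions per patient. Conclude non-inferiority only if the bound lies above the margin. The only candidate in the plan is 15 points. Adopting it is an assumption that needs its own justification, because it equals the deficit the plan expects for calcium. Keep Fisher's test as supportive, and state that its non-significance is not evidence of non-inferiority. Do not carry the 80% power over to the non-inferiority conclusion.

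**If no margin can be justified, or the codes have already been opened.** Remove the non-inferiority declaration, report the difference with its interval, and draw no conclusion about replacement. This needs no re-sizing.

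**Cost.** The text is a margin with its reason, one analysis paragraph and one decision rule. The real cost of the first route is power. At a 15-point margin with both rates 85%, 80% power needs about 52 tumours per arm at one-sided 0.1 (71 at one-sided 0.05), before any allowance for clustering. Otherwise the trial must be accepted as likely to be inconclusive.
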